11.2.3 Definition of hypoglycaemic events

The hypoglycaemic event considered in the primary endpoint will be a composite endpoint of confirmed hypoglycaemia (any severity) as well as major (or severe) hypoglycaemias (with or without confirmed low glucose value) using the following definitions:

Confirmed hypoglycaemia: any events defined as either a symptomatic event with blood glucose level <3 mmol/L (<54 mg/dL) and no need for external assistance, or an asymptomatic blood glucose measurement <3 mmol/L (<54 mg/dL).

Major (or severe) hypoglycaemia: symptomatic events requiring external assistance due to severe impairment in consciousness or behaviour, with or without blood glucose level <3 mmol/L (<54 mg/dL), but with prompt recovery after glucose or glucagon administration. These events may be associated with sufficient neuroglycopenia to induce seizure or coma. Plasma glucose measurements may not be available during such an event, but neurological recovery, attributable to the restoration of plasma glucose to normal, is considered sufficient evidence that the event was induced by a low plasma glucose concentration.

N.B.: Mild or moderate hypoglycaemic events where blood glucose measurement is not available will be considered suggestive of hypoglycaemia but will not be considered in the primary endpoint. (Draft Guidance from FDA (February 2008), EMEA Diabetes Guidance document 2002))

11.2.4 Baseline and change from baseline

Baseline is defined to be Visit 1 for safety variables. Change from baseline will be calculated as absolute difference between the value measured at or derived for a specific time point after baseline minus baseline value.

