Placebo 1 mg 1-2 mg ² 1-3 mg ² 1-4 mg ²						1-6 mg ², 3	Placebo 1 -6 mg							
	E Saxagliptin 5 mg							Saxagliptin 5 mg						
Week	-6	-4	t .	-2	0	3		6	9	12	24	32	40	52
Visit	s	1		2	3	4		5	6	7	8	9	10	11
				Counselling on dietary and lifestyle modifications according to usual clinic al routine									\rightarrow	

1. Lead-in, placebo 1 mg and placebo 5 mg, single blinded treatment for glimepiride and saxagliptin

2. Indicates dose range for the glimepiride/placebo treatment. Should be based on treatment target FPG ≤6.1 mmol/L or ≤110 mg /dL and the patient's self monitored plasma glucose values.

3. The patients reaching the 6 mg dose at Visit 7 will have a follow-up phone call 3 weeks later

Revised Clinical Study Protocol Drug Substance Saxagliptin Study Code D1680L00002 Edition Number 4.0 Date

The study will consist of 4 periods:

Enrolment Period (Week -4 to -2)

Patients aged 65 years or older with type 2 diabetes with inadequate glycaemic control (HbA_{1c} \geq 7.0 % and \leq 9.0% based on value from screening visit) and currently on a stable monotherapy of metformin (any doses) for at least 8 weeks will be eligible to enter the study. The patient should maintain the prescribed stable dose of metformin for the duration of the study. Blood sampling and other examinations for assessment of inclusion and exclusion criteria will be performed.

Lead-in Period (Week -2 to 0)

Patients who still meet all inclusion and no exclusion criteria are eligible to enter the 2-week single-blind (blind to patient only) placebo lead-in period. The patients will from this period on, and during the entire study, be counselled on dietary and lifestyle modifications according to usual clinical routine. They will be given a glucometer to check their plasma glucose at home on a regular basis and to register the results in the patient diary during the duration of the study. The glucometer measures capillary glucose, and the measured value is recalculated by the glucometer to show plasma values. Hypoglycaemic events should during the entire study period always be entered into the patient hypoglycaemic event diary. For details on hypoglycaemic events and diaries, see Sections 6.4.9 and 6.5, 6.5.1.

Titration Period (Week 0 to 12)

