After the titration period, the patient will remain on the patient optimal dose of investigational products for 40 weeks to assess efficacy and safety of the treatment. The dose of glimepiride/placebo can be down titrated at any time during this period to mitigate recurrent hypoglycaemic events at the discretion of the investigator. No up titration will be allowed during the maintenance treatment period (ie, if dose is lowered it will then be left on this lower dose level). Assessment of glycaemic parameters (based on results from central laboratory) will be done at each visit to determine if criteria for discontinuation are met during the period.

The titration period and the maintenance treatment period are referred to as the double-blind treatment period and is 52 weeks long.

Table 1

Study plan for Enrolment, Lead-in, Titration and Maintenance periods

	Screen.	Enrol.	Lead-in	Rand.		Titratio	n Period		Maintenance Treatment Period				
Visit number	S	1	2 ^a	3	4	5	6	7	8	9	10	11 ^b	
Study Week	-6	-4	-2	0	3	6	9	12	24	32	40	52	
Visit Window Day ± No. Days	-42 ± 7	-28 ± 3	-14 ± 3	0	21 ± 3	42 ± 3	63 ± 3	84 ± 3	168 ± 3	224 ± 3	280 ± 3	364 ± 3	
Screening Informed consent and blood sample for determination of HbA_{1c}	Х												
Informed consent		Х											
Medical history and demography		Х											
Inclusion/exclusion criteria		Х	Х	Х									
Physical examination		X										Х	
Brief physical examination				Х									
Blood pressure, pulse rate		X		Х				Х	Х	Х	Х	Х	
Weight		X		Х				Х	Х	X	X	Х	
Height		X											
Waist circumference				Х								Х	
ECG		Х										Х	
Concomitant medication		Х	Х	Х	X	X	Х	X	Х	X	X	Х	
Laboratory assessments ^c		X		Х	X	Х	X	Х	Х	X	Х	Х	
Register titration of glimepiride/placebo during the titration period (if applicable) in IWRS					X	X	X	X					
Patient reported outcomes questionnaires ^d				Х					Х			Х	

Revised Clinical Study Protocol Drug Substance Saxagliptin Study Code D1680L00002 Edition Number 4.0 Date

	Screen.	Enrol.	Lead-in	Rand.	Titration Period				Maintenance Treatment Period				
Visit number	S	1	2 ^a	3	4	5	6	7	8	9	10	11 ^b	
Study Week	-6	-4	-2	0	3	6	9	12	24	32	40	52	
Visit Window Day ± No. Days	-42 ± 7	-28 ± 3	-14 ± 3	0	21 ± 3	42 ± 3	63 ± 3	84 ± 3	168 ± 3	224 ± 3	280 ± 3	364 ± 3	
Register down titration of glimepiride/placebo during the maintenance period (if applicable) in IWRS									Х	Х	Х		
Dispense investigational products			Х	Х	Х	Х	Х	Х	X	Х	Х		

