Dispense glucometer and/or supplies/provide instruction			Х	Х	Х	Х	Х	Х	X	Х	Х		
Dispense patient diaries			Х	Х	Х	Х	Х	Х	Х	Х	Х		
Patient diary review for hypoglycaemic events/check glucometer values				Х	Х	Х	Х	Х	X	Х	Х	Х	
Adverse Events (AEs)				Х	Х	Х	Х	Х	Х	Х	Х	Х	
Serious Adverse Events (SAEs) ^e		Х	X	Х	Х	Х	Х	Х	Х	Х	Х	Х	
Drug accountability ^f				Х	Х	Х	Х	Х	Х	Х	Х	Х	

a. Visit 2 may be performed as a telephone visit if it is clear before the visit that the patient is not eligible due to the laboratory results

b. Randomised patients who do not complete the entire study should complete the procedures described for Visit 11

c. Specification of laboratory parameters are shown in Table 2 and Table 3

d. Patient reported outcomes questionnaires: DTSQ, HFS-II, EQ-5D

e. From the time when the Informed Consent is obtained (Visit 1) until the first administration of investigational products (Visit 3), only SAEs need to be recorded

f. Returned tablets should be counted and the number of returned tablets and date of return should be registered in the eCRF

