3.2.4 Choice of outcome variables

While HbA_{1c} is traditionally used as a primary endpoint in these types of clinical trials, it was felt that a primary endpoint that would be including both HbA_{1c} and hypoglycaemia (confirmed or severe) would be more appropriate, as the clinical treatment decision ultimately takes into account those two factors in real practice. HbA_{1c} is also a recommended efficacy variable in regulatory diabetes guidelines. As a member of DPP-4 inhibitors, saxagliptin leads to enhanced glucose dependent insulin secretion: low risk of hypoglycaemia and minimal weight gain may be expected. As a result, the present study will be examining other secondary efficacy outcome variables: weight, β -cell function measured by HOMA- β . It is believed that saxagliptin treatment may protect and/or promote pancreatic β -cell function, hence the saxagliptin therapy may be more durable and patients may have a better insulin secretion over time compared to glimepiride as an add-on therapy to metformin.

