6.3 Efficacy

The baseline is defined as the assessment at randomisation visit (Visit 3).

Self-monitoring of plasma glucose should be done in order to reduce risk of prolonged periods of undetected hyperglycaemia or to confirm hypoglycaemia. Patients will be asked to do self-monitoring of plasma glucose using glucometers provided by AstraZeneca. The patients will receive instruction on the use of the glucometer, according to the manufacturer's instruction.

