11. EVALUATION AND CALCULATION OF VARIABLES BY ASTRAZENECA

11.1 Calculation or derivation of efficacy variable(s)

11.1.1 Baseline and change from baseline

Baseline is defined to be Visit 3 (randomisation). Change from baseline will be calculated as absolute difference between the value measured at or derived for a specific time point after baseline minus baseline value.

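### Section 11.2.4 takes Visit 1 as baseline for weight, blood pressure and pulse, although all three are measured again at Visit 3, before double-blind dosing

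*Protocol*

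**What the plan says.** The protocol has two baseline rules.

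- Safety, section 11.2.4: "Baseline is defined to be Visit 1 for safety variables". The rule has no exception by variable.
- Efficacy, section 11.1.1: "Baseline is defined to be Visit 3 (randomisation"). Section 6.3 agrees: "The baseline is defined as the assessment at randomisation visit (Visit 3").

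Table 1 in section 3.1 places Visit 1 at Day -28 ± 3 and Visit 3 at Day 0. Its footnote on serious adverse events ties the start of randomised product to Visit 3 ("until the first administration of investigational products (Visit 3"). The row "Blood pressure, pulse rate" and the row for weight are both marked at Visits 1, 3, 7, 8, 9, 10 and 11.

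Section 2.3 lists blood pressure, pulse rate and body weight among the safety assessments. Section 3.2.4 nevertheless places weight among "other secondary efficacy outcome variables: weight". Section 3.1 says that from the lead-in period (Week -2) onwards patients will "be counselled on dietary and lifestyle modifications according to usual clinical routine".

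Section 12.2.2 analyses exploratory continuous endpoints by ANCOVA on change from baseline, with the baseline value as covariate. It reports within-group mean changes with 95% confidence intervals as well as the difference between groups.

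**The concern.** A baseline is normally the last value before the treatment under study begins. For weight, blood pressure and pulse the protocol collects such a value at Visit 3 and then passes over it for one taken four weeks earlier. In those four weeks patients start single-blind placebo and dietary and lifestyle counselling. Any response to these, and any other drift, is then reported as change from baseline on treatment within each arm.

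Weight matters most. Section 3.2.4 expects minimal weight gain with saxagliptin, and section 1.3 names weight gain as a side effect of some insulin secretagogues, so the protocol itself treats weight as an outcome on which the drugs may differ. Weight also falls under both baseline rules, depending on whether 2.3 or 3.2.4 is followed, and no text says which prevails. That leaves a choice between two covariates and two sets of reported changes.

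**Working it through.** The protocol gives no figure to reproduce here, so the check matches the rule in 11.2.4 to the visit schedule.

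**Step 1. Last assessment before double-blind dosing** (Table 1, Table 3, sections 6.4.6 and 6.4.7):

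| Variable | Visit 1 (Day -28) | Visit 3 (Day 0) | Last pre-dose value |
|---|---|---|---|
| Weight, blood pressure, pulse | yes | yes | Visit 3 |
| Waist | no | yes | Visit 3 |
| Safety laboratory variables | yes | no | Visit 1 |
| ECG | yes | no | Visit 1 |
| Full physical examination | yes | no (brief examination only) | Visit 1 |

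The Visit 1 rule is right for the last three rows, and 6.4.6 itself names Visit 1 as baseline for the physical examination. It does not suit the first row.

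**Step 2. Share of the change interval that precedes randomised treatment.** With baseline at Visit 1, the share at study day d is 28 / (d + 28).

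| Visit | Day d | Span from Visit 1 (days) | Pre-treatment share |
|---|---|---|---|
| 7 (Week 12) | 84 | 112 | 28/112 = 25.0% |
| 8 (Week 24) | 168 | 196 | 28/196 = 14.3% |
| 9 (Week 32) | 224 | 252 | 28/252 = 11.1% |
| 10 (Week 40) | 280 | 308 | 28/308 = 9.1% |
| 11 (Week 52) | 364 | 392 | 28/392 = 7.1% |

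With the ±3-day window on Visit 1 the gap is 25 to 31 days. At Week 52 the share then runs from 25/389 = 6.4% to 31/395 = 7.8%, and at Week 12 from 25/109 = 22.9% to 31/115 = 27.0%. The change to Week 52 spans 392/7 = 56 weeks instead of 364/7 = 52. The lead-in and the counselling occupy the last 14 of the 28 days.

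**Step 3. Between-arm contrast.** Write the change from Visit 1 as (Visit 11 − Visit 3) + (Visit 3 − Visit 1). The second term is complete before randomised treatment starts, so its expectation is the same in both arms and cancels in the difference. The contrast is not biased. The within-arm means do shift, each by the mean of the second term.

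**Step 4. Precision where ANCOVA is used.** With the baseline as covariate, residual variance is proportional to 1 − r², where r is the correlation between baseline and the Week 52 value. The ratio for Visit 1 against Visit 3 is (1 − r1²) / (1 − r3²). The protocol gives no correlations, so these values are assumptions that only show how the ratio behaves:

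- r3 = 0.90, r1 = 0.89: 0.2079/0.1900 = 1.09
- r3 = 0.90, r1 = 0.85: 0.2775/0.1900 = 1.46
- r3 = 0.70, r1 = 0.69: 0.5239/0.5100 = 1.03
- r3 = 0.70, r1 = 0.65: 0.5775/0.5100 = 1.13

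The range is wide because it depends almost wholly on the assumed correlations.

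**Step 5. Weight under the two rules.** Sections 2.3 and 11.2.4 together give Visit 1. Sections 3.2.4, 6.3 and 11.1.1 together give Visit 3. Both cannot be followed.

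**The case against.** The strongest reply is that the main result of a randomised active-controlled trial is the difference between arms, and that this is preserved (step 3). That stands in full. Three further points also stand.

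- The rule is correct for safety laboratory variables, ECG and the full physical examination. Moving everything to Visit 3 would leave those without a baseline.
- The second baseline for weight comes from one sentence of rationale in 3.2.4. The synopsis and 2.2 list the secondary efficacy endpoints without weight, and the synopsis and 2.3 put it under safety. A loose label is the likelier explanation than two intended definitions, but the text still needs to be reconciled.
- Section 12.2.2 applies ANCOVA to exploratory continuous endpoints and does not say that blood pressure and pulse are modelled. The covariate argument therefore holds only where ANCOVA is used.

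A reader might also infer that change in waist cannot be computed, because the row "Waist circumference" in Table 1 is marked only at Visits 3 and 11. The protocol does not support that as a defect. Waist appears in no list of safety variables and in no objective, and no analysis of its change is promised. Its only link to the safety rule is its place in 6.4.8, which also covers height, a measurement taken once. The waist schedule matters only if its change is to be summarised.

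A reader might want a definite loss of precision. A random-walk model, for instance, would give 56/52 = 1.077, or about 8% more variance of change. Nothing in the protocol supports that model, and it would be hard to defend for blood pressure and pulse, where noise around a stable level is more plausible.

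**Conclusion.** The point holds as a minor one. For weight, blood pressure and pulse the stated baseline is about 28 days earlier than it need be. Reported within-arm changes therefore include a pre-treatment stretch equal to 7% of the span to Week 52 and 25% of the span to Week 12. These shares are proportions of time, not of effect: how far the values actually move between Visit 1 and Visit 3 is not known from the protocol. Some precision is lost where the baseline is a covariate, and its size cannot be derived from the document. Weight is also subject to two conflicting baseline rules.

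The documents do not support a stronger reading. The treatment comparison is not biased, and the primary endpoint, the key secondary endpoint, the type I error rate and the sample size are untouched. The conclusion assumes that the Visit 3 measurements are made before the first double-blind dose. This fits section 5.5.2, under which product is not taken on the morning before a visit. The SAP was not available and might refine the rule, but the protocol states it outright, so this is more than detail left open.

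**What to change.** Replace the first sentence of 11.2.4 with a rule by variable, for example:

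> For weight, BMI, blood pressure and pulse, baseline is the last value before the first double-blind dose: Visit 3, or Visit 1 if the Visit 3 value is missing and a Visit 1 value exists. The same rule applies to waist if its change is summarised. For safety laboratory variables, ECG and the full physical examination, baseline is Visit 1.

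Waist has no Visit 1 value, so a patient without a Visit 3 waist measurement would have no baseline for it.

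Also bring 3.2.4 into line with 2.3 on whether weight is an efficacy or a safety variable. Under the revised rule the baseline is Visit 3 on either label.

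The cost is a short edit, best made before unblinding. The Visit 3 values are already scheduled for every randomised patient, so there is no added visit, sample or patient burden, and no effect on sample size or error control.

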11.3 Calculation or derivation of patient reported outcome variables

Method of assessment and purposes of patient reported outcomes (PRO) variables are presented in Section 6.5.4.

11.3.1 Diabetes Treatment Satisfaction Questionnaire (DTSQ)

In the DTSQs, the individual satisfaction with treatment items (1, 4, 5, 6, 7 and 8) are rated 6 (very satisfied, convenient, flexible etc) to 0 (very dissatisfied, inconvenient, inflexible etc) and added up to a Treatment Satisfaction score (range 0-36). The higher the score, the greater the satisfaction with treatment.

'Perceived frequency of hyperglycaemia' (Item 2) and 'Perceived frequency of hypoglycaemia' (Item 3) are rated 6 (most of the time) to 0 (none of the time). Lower scores indicate levels closer to the ideal and higher indicate problems.

These scores from the DTSQs, assessed at Visit 3, will be presented.

In the DTSQc, the individual satisfaction with treatment change items (1, 4, 5, 6, 7 and 8) are rated +3 (improvement) to -3 (deterioration) and added up to a Treatment Satisfaction (change) score (range +18 to -18). The higher (lower) the score, the greater the improvement (deterioration) in satisfaction with treatment. A score of 0 represents no change.

'Perceived frequency of hyperglycaemia' (Item 2) and 'Perceived frequency of hypoglycaemia' (Item 3) are rated +3 ('much more of the time now') to -3 ('much less of the time now'). Negative score indicate fewer problems with blood glucose levels. Positive scores indicate more problems than before.

These scores from the DTSQc assessed at Visit 8 and Visit 11 will be presented.

11.3.2 Hypoglycaemia Fear Survey-II (HFS-II) Worry Subscale

The HFS-II worry subscale consists of 18 items, rated by patients from 0 (never) to 4 (almost always). Scores are obtained by the sum of all the responses on the scale and range from 0 to 72, with 0 representing least worry. The score from HFS-II assessed at Visit 3, Visit 8 and Visit 11 will be presented.

11.3.3 EuroQoL-5 Dimension (EQ-5D)

The EQ-5D self-report questionnaire comprises two parts: the EQ VAS, which records an overall rating of health from 0-100 on a visual analogue scale (0=worst possible health to 100=best possible), and the EQ-5D self-classifier, which includes five dimensions (mobility, self-care, usual activity, pain/discomfort and anxiety/depression) with three levels each (no problems, some problems and severe problems). The EQ-5D index is constructed by applying utility weights to each of the levels within each dimension and adding these together. Utility weights are elicited from general population surveys that used one of the available direct utility assessment methods.

The EQ VAS and EQ-5D index will be presented at Visit 3, Visit 8 and Visit 11.

- **11.4** Calculation or derivation of pharmacokinetic variables (Not applicable)
- 11.5 Calculation or derivation of pharmacodynamic variable(s) (Not applicable)
- 11.6 Calculation or derivation of pharmacogenetic variables (Not applicable)
- 11.7 Calculation or derivation of health economic variables (Not applicable)

12. STATISTICAL METHODS AND SAMPLE SIZE DETERMINATION BY ASTRAZENECA

The primary objective of the study will be to show the superiority of saxagliptin compared to glimepiride in elderly patients (\geq 65 years) with type 2 diabetes in regard to the proportion of patients achieving the HbA_{1c} target of <7% without hypoglycaemia (confirmed or severe) after 52 weeks of treatment. Any patient who does not complete the 52-week treatment period will be considered as a non-responder, ie, as having not achieved the HbA_{1c} target without confirmed or severe hypoglycaemia. For definition of hypoglycaemic events, see Section 11.2.3.

The key secondary objective (safety analysis) will be to show the superiority of saxagliptin compared to glimepiride in regard to the proportion of patients having experienced at least one hypoglycaemic event (confirmed or severe) over the 52-week treatment period. A hierarchical testing procedure will be applied in order to control the type I error rate.

12.1 Description of analysis sets

Efficacy analyses for the primary endpoint will use the safety analysis set. The safety endpoints will be analysed from the safety analysis set.

A detailed description of analysis sets is given below. The decision to include or exclude patients from each analysis set will be performed in a blind data review prior to unblinding. A summary of the number of patients per analysis set will be given and reasons for exclusion of a patient from an analysis set will be listed.

12.1.1 Lead-in analysis set

For the summary of patients enrolled to the lead-in period, all patients who enrolled to the lead-in period with an E-code and took at least one placebo dose during the lead-in period will be included in the lead-in analysis set.

12.1.2 Randomised analysis set

For the summary of baseline characteristics, all patients with a randomisation number will be included in the analysis set.

12.1.3 Full analysis set (FAS)

The full analysis set is defined for the analyses of exploratory efficacy endpoints as the subset of randomised analysis set including patients who took at least one randomised investigational

product dose, have non-missing baseline and post-baseline efficacy data.

12.1.4 Per protocol (PP) analysis set

The PP analysis set is defined as a subset of the full analysis set including patients with no reason for exclusion. A PP analysis on the primary variable will only be performed if more than 10% of the patients in any regimen are found to significantly violate the terms and conditions of the protocol. Otherwise, analysis of the primary variable will be restricted to the safety analysis set.

These exclusions from the PP analysis set will include but not be limited to the patients who took prohibited concomitant medications, non-compliance to investigational products and significant deviations of study procedures. The exclusions from the PP analysis set will be explicitly defined in the Statistical Analysis Plan (SAP) before breaking the blind.

